Aim 2: Examine candidate mechanisms underlying the effect of eIMPACT on CVD risk. Depressed patients randomized to eIMPACT, versus usual care, will exhibit greater decreases in the secondary outcomes of depressive symptoms (Hypothesis 2), autonomic dysfunction (Hypothesis 3), systemic inflammation (Hypothesis 4), and platelet activation (Hypothesis 5) at the 12-month post-treatment visit. We will also explore whether decreases in these four candidate mechanisms (a) are associated with improvements in endothelial dysfunction and (b) are partial mediators of eIMPACT's hypothesized cardioprotective effect.

A positive trial would generate the mechanistic rationale, efficacy evidence, and effect size estimates needed to justify and design a multisite, event-driven Phase 3 trial to confirm eIMPACT's efficacy in reducing CVD risk. Conversely, a negative trial would indicate a need to evaluate alternative approaches to reducing the excess CVD risk of depressed patients. Demonstrating that depression treatment reduces CVD risk, the main expected outcome of this line of research, would have a substantial positive impact. It would identify a novel target (depression) for CVD prevention efforts, and it would equip providers with a new disseminable and scalable tool (eIMPACT) to treat depression and manage the CVD risk of a large cohort of high-risk patients. These clinical practice changes should translate into reduced CVD morbidity, mortality, and costs, as our preliminary results suggest that treating 1,000 depressed adults may prevent 164 CVD events over 5 years.³⁵

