8.0 Statistical Considerations

Sample Size and Power Considerations

Endothelial Dysfunction

Using the effect size of depression treatment on FMD from our pilot trial, we need 88 patients (44 per arm) to detect a group difference in FMD of 1.7% ($d = 0.61$) at 12 months, assuming a power level of 0.80 and a Type I error of 0.05. This would be a clinically relevant difference. Assuming a conservative attrition rate of 20%,²⁰⁴ we will have 172 completers ($220 \times .80$) for FMD, yielding power levels of 0.98 for $d = 0.61$ and 0.80 for $d = 0.43$.

Candidate Mechanisms

We expect at a power level ≥ 0.80 for the candidate mechanisms (Hypotheses 2-5), as we will be able to detect effect sizes as small as $d = 0.43$ with 172 completers. In our IMPACT study³⁵ and pilot trial, effect sizes for depressive symptoms ($d = 0.69$ and 1.33), IL-6 ($d = 0.43$), and CRP ($d = 0.78$) were in the medium-to-large range. In other studies, effect sizes of 0.52 were found for psychological interventions on heart rate variability,²⁰⁵⁻²⁰⁷ 1.00 for SSRIs on IL-6,¹⁴³ 0.74 for SSRIs¹⁴³ and 0.85 for CBT¹³⁸ on CRP, 0.91¹⁴⁶ and 0.46¹⁴⁴ for SSRIs on BTG, and 0.87 for SSRIs on PF4.¹⁴⁴

CVD Events

Over the mean observation period of 4 years, we anticipate a cumulative CVD event rate of 20% (39 events) and a 25% lower relative risk ($HR \leq 0.75$) in eIMPACT versus usual care. These estimates are reasonable, as we observed a CVD event rate of 24% and a 46% lower relative risk (event rate: 18% vs. 31%) in our IMPACT secondary analysis that had a 4-year observation period. Our high-risk sample will differ from the typical sample of a risk reduction trial in that (a) all patients will have depression and ≥ 1 CVD risk factor and (b) many will be of low SES and/or African American, two groups at elevated risk for CVD event.^{1,171} Although we expect to have CVD event data for nearly all patients, we assume a conservative attrition rate of 10%, leaving 194 completers. As is typical of Phase 2 trials, our trial is not designed to detect a statistically significant difference in clinical events; however, a 25% relative risk reduction would be a clinically relevant signal (statin therapy reduces risk by $\approx 30\%$ ¹⁵⁶) and has been used to power recent event-driven Phase 3 cardiology trials.¹⁵⁷

Statistical Analyses

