We will use the intent-to-treat approach.²⁰⁸ All tests will be two-tailed with $p < .05$ considered significant. Supplemental analyses of completers will be performed. We will assess for differences in all baseline factors. Due to randomization, we do not expect baseline group differences. Even so, any differences will be taken into account when interpreting results, and any baseline factors that differ between the groups will be included as covariates in sensitivity analyses. Aim 1: We will test our hypothesis that eIMPACT patients will exhibit greater improvement in endothelial dysfunction (Hypothesis 1) by performing a two-sample t-test with FMD at 12 months as the dependent variable. If there is a group difference in baseline FMD, analyses of covariance (ANCOVAs) adjusting for baseline level will also be performed. We will also explore whether eIMPACT patients show a clinically relevant reduction (25% lower relative risk) in CVD events by running a Cox proportional hazards model with treatment group predicting time to first CVD event. Patients will be censored at non-CVD death or the end date. We expect to observe a $HR \leq 0.75$. Aim 2: We will test our hypotheses that eIMPACT patients will exhibit greater decreases in the candidate mechanisms (Hypotheses 2-5) by performing two-sample t-tests with SCL-20 score, high-frequency heart rate variability, IL-6, CRP, BTG, and PF4 at 12 months as the dependent variables. If baseline group differences are found, ANCOVAs adjusting for baseline level will

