also be performed. To explore whether decreases in the candidate mechanisms are associated with improvements in endothelial dysfunction, we will compute correlations between 12-month change in each mechanism and in FMD. To explore whether decreases in the candidate mechanisms are partial mediators of eIMPACT's hypothesized cardioprotective effect, we will conduct exploratory mediation analyses using MacKinnon's approach, which has greater power than others.²⁰⁹ First, to quantify the treatment effect on each mechanism ("a" coefficients), we will perform linear regressions with treatment group predicting 12-month level of each mechanism. Second, to quantify the effect of each candidate mechanism on endothelial dysfunction ("b" coefficients), we will perform linear regressions with 12-month level of each mechanism predicting 12-month FMD in the presence of treatment group. Third, the significance of each mediation effect will be tested using MacKinnon and Lockwood's product of coefficients ("ab") method employing asymmetric confidence limits.^{209,210} If this test is significant, the selected mechanism is a partial mediator of the treatment effect on 12-month FMD. Of note, we will also explore (a) if changes in depressive symptoms are correlated with changes in the atherogenic physiologic factors and (b) if changes in FMD predict CVD events.

Supplemental, Hypothesis-Generating Analyses

(1) We will explore atherogenic behavioral factors, conventional CVD risk factors, and depression care variables as potential mechanisms of eIMPACT's effect on FMD by repeating Aim 2 analyses. (2) To explore the separate effects of intervention components (which likely have shared and unique pathways; Figure 1), Aim 1 and 2 analyses will be repeated after coding the treatment variable as follows: eIMPACT both components, eIMPACT antidepressants only, eIMPACT psychotherapy only, eIMPACT neither component, and usual care. (3) We will explore sex and race/ethnicity as moderators of the treatment effect on the outcomes. (4) We will estimate the cost per patient of providing eIMPACT, including charges for BtB, DCS, psychiatrist and primary care expert supervision, materials, and a telephone line.

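### The exploratory change-on-change correlations carry no treatment-group term, so they mix the arm effect with any within-arm association

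*Combined protocol and SAP*

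**What the plan says.** Section 2.0 sets the exploratory question in Aim 2: "We will also explore whether decreases in these four candidate mechanisms (a) are associated with improvements in endothelial dysfunction". The Statistical Analyses part of section 8.0 gives the method. It repeats the purpose, "To explore whether decreases in the candidate mechanisms are associated with improvements in endothelial dysfunction", and then states that "we will compute correlations between 12-month change in each mechanism and in FMD". A few lines later it adds a second exploratory set, asking "if changes in depressive symptoms are correlated with changes in the atherogenic physiologic factors".

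Neither sentence mentions treatment group, stratification, partial correlation or baseline adjustment. The mediation step between them does name the arm. Its second regression has "12-month level of each mechanism predicting 12-month FMD in the presence of treatment group", although it uses 12-month levels rather than changes.

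The power paragraphs of section 8.0 expect a treatment effect on FMD (d = 0.61) and on all the candidate mechanisms, with quoted effect sizes from 0.43 to 1.33.

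**The concern.** The text does not use the word pooled. Still, the authors name treatment group where they want it, and here they do not, so a single correlation across all completers is the natural reading.

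If treatment shifts both variables, the two arms form two clouds with different centres. The line joining the centres produces a correlation even when, inside each arm, patients whose mechanism improves more gain no more FMD. That component only restates Hypothesis 1 together with the relevant one of Hypotheses 2-5. It adds nothing on whether the mechanism tracks endothelial function from patient to patient.

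The same applies to symptom change against physiologic change. The conceptual framework in section 1.0 proposes that some antidepressants act on inflammation and platelet activation directly, apart from symptom relief. Such parallel effects would give a pooled correlation with no link from symptoms to physiology.

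The stake is interpretive. Section 1.0 intends to use identified mechanisms to choose adjunctive treatments and to justify a Phase 3 trial.

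**Working it through.** **Inputs from section 8.0.** FMD d = 0.61. Mechanism d: IL-6 0.43; heart rate variability 0.52; SCL-20 0.69 and 1.33; CRP 0.78; PF4 0.87; BTG 0.91. Two-sided 5% tests and equal arms ("All tests will be two-tailed"; "we need 88 patients (44 per arm"). 172 completers as printed; 220 × 0.80 is 176, which makes no material difference here.

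**Assumptions not in the documents.** Within-arm correlation of the two changes = 0. The d values apply to change scores, which holds if the baseline-to-12-month correlation is 0.5; the range 0.3 to 0.7 is examined below.

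**The plan's own figures first.** The t-based sample size for d = 0.61 at 80% power is 43.2 per arm, rounded up to 44, or 88 in all. With 86 per arm, t-based power is 0.978 at d = 0.61 and 0.801 at d = 0.43. The printed 88, 0.98 and 0.80 all reproduce. The plan gives no figure for the correlations.

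**Induced correlation.** With equal arms and unit within-arm SD, the arm difference adds d²/4 to each variance and d₁d₂/4 to the covariance, so

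|r| = (d₁d₂/4) / √[(1 + d₁²/4)(1 + d₂²/4)].

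For SCL-20 at 0.69 and FMD at 0.61: 0.1052 / √(1.1190 × 1.0930) = 0.1052 / 1.1059 = 0.095.

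**Rejection rate by Fisher z.** √(172 − 3) = 13. For |r| = 0.095, 13 × 0.0954 = 1.24, and the chance of exceeding 1.96 is about 24%. Simulation (20,000 replicates, N = 172) gives 23%. The critical |r| is 0.150.

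Simulation results at N = 172 with FMD d = 0.61:

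| Mechanism | d | Pooled abs. r | Pooled test rejects |
|---|---|---|---|
| IL-6 | 0.43 | 0.061 | 13% |
| Heart rate variability | 0.52 | 0.073 | 15% |
| SCL-20 | 0.69 | 0.095 | 23% |
| CRP | 0.78 | 0.106 | 28% |
| PF4 | 0.87 | 0.116 | 34% |
| BTG | 0.91 | 0.121 | 35% |
| SCL-20 | 1.33 | 0.162 | 57% |

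With FMD d = 0.43 instead, |r| runs from 0.044 to 0.116 and rejection from 9% to 33%.

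**Conversion to change scores.** If SDs are equal at both visits, d for change = d / √[2(1 − ρ)].

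- ρ = 0.3: FMD becomes 0.516 and the mechanism range becomes 0.363 to 1.124. |r| is 0.045 to 0.122 and rejection 9% to 36%.
- ρ = 0.7: FMD becomes 0.788 and the mechanism range becomes 0.555 to 1.717. |r| is 0.098 to 0.239 and rejection 24% to 90%.

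**Checks.** If treatment affects only one of the two variables, the pooled test rejects 5% of the time, so an effect on both is needed. After removing arm means, which is the partial correlation given arm, rejection is 4.7% to 5.3% in every scenario.

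**The case against.** The strongest reply is that a pooled correlation is a legitimate quantity. Aim 2(a) asks about association without saying within arm, and an association carried by treatment is a real association in the trial sample. Rejecting more than 5% of the time is a false-positive rate only against the null of no within-arm association, which the plan does not name. This stands. A reader might infer that the analysis cannot answer its question at all, and that goes too far. The pooled r answers a marginal question; it cannot say how much of the answer is the arm effect.

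A reader might also infer that success on Hypotheses 1 and 2 would by itself turn these correlations positive. The figures do not support that. At d = 0.69 and 0.61 the artefact alone is non-significant about three times in four. Only the pilot value of 1.33 takes rejection above one half under the base assumption. The largest induced r there, 0.16, is about 2.6% of variance (0.162² = 0.026).

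Nor do the documents say that a significant correlation would be taken as proof of a mechanism. The only interpretive rule belongs to the mediation test. That step already includes an arm-adjusted regression of FMD on each mechanism, so part of the question is covered. It uses 12-month levels, however, and leaves the change correlations as they are.

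Finally, pooling is inferred from silence. If arm-adjusted or within-arm correlations were intended, one sentence would settle it.

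**Conclusion.** The point holds as a minor improvement to exploratory analyses. On the plain reading, both sets of change correlations are pooled over arms. If eIMPACT works as expected on both variables, they blend the arm effect with any within-arm association. With no within-arm association and FMD d = 0.61, |r| is about 0.06 to 0.16 and a 5% test rejects about 13% to 57% of the time at N = 172. These figures depend on applying the plan's d values to change scores, which the plan does not state it intends. Over baseline-to-12-month correlations of 0.3 to 0.7 the range is about 9% to 90%, so the size is uncertain while the direction is not. The FMD primary test, Hypotheses 2-5, the sample size and the arm-adjusted mediation regression are unaffected.

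**What to change.** In the Statistical Analyses part of section 8.0, state for both sets that the association between changes will be estimated by partial correlation, or by regression of change on change, adjusting for treatment group and preferably for the baseline values of both variables. Report within-arm estimates with confidence intervals alongside; 172 completers give 86 per arm. A group-by-mechanism term can check whether the slopes differ. If an unadjusted pooled correlation is kept, describe it only as a marginal association. The supplemental analyses that repeat Aim 2 for behavioural factors, conventional risk factors and depression care variables should follow the same rule. The cost is one or two sentences of plan wording; all the data are already due to be collected.

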Because depression satisfies 8 of Hill's 9 criteria for causation,¹⁸ it is reasonable to conclude that depression is an independent, and potentially causal, risk factor for CVD. Experimental animal research also supports a causal relationship between depression and atherogenesis.¹⁹ The lack of experimental evidence in humans, however, prevents one from drawing a causal inference, as the possibility that a third factor (e.g., genetic variants related to inflammation) explains the depression-CVD association has not been ruled out.²⁰

The Problem: Attempts to improve CVD outcomes of depressed patients have been unsuccessful.

Despite this strong evidence base, the few trials that have evaluated whether depression interventions reduce the likelihood of CVD events generally have not observed the anticipated benefits. A key study was the Enhancing Recovery in Coronary Heart Disease (ENRICHD) Patients trial, in which 2,481 post-MI patients with depression and/or low social support were randomized to cognitive-behavioral therapy (CBT) or usual care. After 29 months, no difference in nonfatal MI or death was found.²¹ In the Sertraline Antidepressant Heart Attack Randomized Trial (SADHART), depressed CAD patients randomized to selective serotonin reuptake inhibitor (SSRI) treatment had a numerically lower rate of CVD events than patients randomized to placebo.²² This suggestive trend was not confirmed in the Myocardial Infarction and Depression Intervention Trial (MIND-IT), in which depressed post-MI patients were randomized to a staged pharmacologic intervention or usual care.²³ Follow-up studies of ENRICHD, SADHART, and MIND-IT confirmed the absence of intervention effects on medical outcomes.²⁴⁻²⁶ Interestingly, some post hoc analyses of these trials revealed that patients whose depression improved had better long-term medical outcomes.^{24,25,27} However, other researchers have suggested that these relationships may be due to confounding, as early improvements in medical status after a CVD event may predict both later improvements in depressive symptoms and a reduced likelihood of recurrent CVD events.^{28,29} This would explain the null intervention effects in these trials.

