The atherogenic physiologic and behavioral factors in Figure 1 are the leading candidate mechanisms through which depression treatment may reduce CVD risk. Substantial literatures indicate that depression is reliably associated with each factor,¹²⁰⁻¹²⁶ as well as endothelial dysfunction.⁵¹ Although far fewer in number, some studies have reported more direct evidence. We and others have observed that the strength of the depression-CVD association is attenuated after adjusting for autonomic function indices,^{127,128} inflammatory markers,¹²⁸⁻¹³⁰ physical activity,¹³⁰⁻¹³³ and smoking.^{15,130,131,133} Finally, evidence suggests that CBT and SSRIs decrease autonomic dysfunction,¹³⁴⁻¹³⁷ inflammation,¹³⁸⁻¹⁴³ platelet activation,¹⁴⁴⁻¹⁴⁷ and smoking.^{148,149} While we propose that treatment-related reductions in depressive symptoms (paths a and b) will result in decreases in the atherogenic factors (paths d and e), we also hypothesize that SSRIs and SNRIs will reduce CVD risk via their

direct effects on inflammation and platelet activation (path c).^{33,147,150}

We chose the physiologic factors as secondary outcomes, given that they represent likely pathways through which behavioral factors increase CVD risk (path f). This conceptualization is in line with current models of the depression-CVD relationship¹⁵¹ and empirical findings.¹⁵²⁻¹⁵⁵ We will examine behavioral factors as mechanisms in exploratory analyses.

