At the end of the pre-treatment visit described below, the randomization procedure will be initiated. To balance the groups on two strong FMD correlates,⁹¹ randomization will be stratified by sex and age (50-59 and 60+ years) using random number sequences.¹⁶⁸ Sequentially numbered sealed envelopes containing group assignment will be prepared by the study statistician ([name]).

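### The exploratory mediation models adjust only for arm, so a non-causal mechanism–FMD correlation that lasts to 12 months can be reported as partial mediation

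*Combined protocol and SAP*

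**What the plan says.** The Statistical Analyses part of section 8.0 states that "we will conduct exploratory mediation analyses" for the candidate mechanisms. The *a* model regresses the 12-month mechanism on treatment group. The *b* model is "linear regressions with 12-month level of each mechanism predicting 12-month FMD in the presence of treatment group". Neither names a further covariate. The product *ab* is tested with asymmetric confidence limits, and the rule is: "If this test is significant, the selected mechanism is a partial mediator of the treatment effect on 12-month FMD".

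Elsewhere in the same section, "any baseline factors that differ between the groups will be included as covariates in sensitivity analyses", and ANCOVAs on baseline level are added if the arms differ at baseline. Correlations between 12-month change in each mechanism and change in FMD are planned separately and play no part in the mediation rule.

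The protocol recognises rival explanations. Section 1.0 says that "the possibility that a third factor (e.g., genetic variants related to inflammation) explains the depression-CVD association has not been ruled out". It also notes suggestions that confounding explains why patients whose depression improved in earlier trials had better medical outcomes. Section 4.0 stratifies by sex and age to "balance the groups on two strong FMD correlates".

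**The concern.** Assignment is random, so arm is independent of every prior characteristic and *a* is protected. The 12-month mechanism level is not assigned at random. Within an arm, patients with higher inflammation or more depressive symptoms may have lower FMD for reasons that predate the trial, and *b* absorbs whatever part of that association is still present at 12 months. If treatment also moves the mechanism, *ab* can be significant when the mechanism has no effect on FMD.

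The rules triggered by arm differences do not address this, because a common cause of mechanism and FMD can be perfectly balanced between arms and still bias *b*.

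What is at stake is the mechanism conclusion. Mediation is the planned analysis closest to the part of the central hypothesis (section 2.0) that says how eIMPACT works. Section 1.0 foresees adding treatments aimed at whichever mechanisms are identified. The supplemental analyses repeat the Aim 2 approach for behavioural factors, conventional risk factors and depression care variables, so the same models recur.

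**Working it through.** **Plan's own figures.** Section 8.0 says "we will have 172 completers" and gives power 0.98 for d = 0.61 and 0.80 for d = 0.43. With 86 per arm and two-sided 0.05, the t-test gives 0.978 and 0.801, so both reproduce. (220 × 0.80 is 176, not 172; the difference does not matter here.) The plan states no figure for the mediation test.

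**Inputs from the plan.** n = 172; two-sided 0.05; effect of arm on the mechanism 0.43 SD (smallest detectable) or 0.69 SD (depressive symptoms in the earlier IMPACT study). Power for *a* is then 0.80 or 0.99, so a detectable *a* is what the plan expects.

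**Correlation needed for a significant *b*.** The *b* model has three coefficients, so df = 172 − 3 = 169 and t(0.975, 169) = 1.974:

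|r| = t / √(t² + df) = 1.974 / √(3.897 + 169) = 1.974 / 13.149 = 0.150 (0.148 with 176).

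**False label by size of the non-causal 12-month correlation.** Simulation with 86 per arm, true mechanism effect on FMD zero, Monte Carlo asymmetric limits for *ab*, 4,000 trials per cell:

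| Within-arm correlation (absolute) | a = 0.43 | a = 0.69 |
|---|---|---|
| 0 | 3% | 5% |
| 0.05 | 7% | 9% |
| 0.10 | 18% | 25% |
| 0.15 | 37% | 49% |
| 0.20 | 56% | 75% |
| 0.30 | 76% | 97% |

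**From a baseline correlation to a 12-month one.** The documents do not give this step, so it rests on assumption: mechanism stability (sm) 0.5 or 0.7, FMD stability (sf) 0.5 or 0.6. The one related figure, in section 5.0, is an FMD intraclass correlation of 0.70 over 1–4 weeks in 11 healthy volunteers. Two structures were used:

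- *Carry-over*: each variable depends on its own baseline, so the 12-month correlation is r × sm × sf. For r = −0.2 this runs from −0.2 × 0.5 × 0.5 = −0.05 to −0.2 × 0.7 × 0.6 = −0.084.
- *Stable traits*: correlated traits lie behind both visits, so r persists in full. The trait correlation required is r / √(sm × sf): for r = −0.2, from −0.2/√0.42 = −0.31 to −0.2/0.5 = −0.40.

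False-label rates over the eight combinations (1,000 trials each), planned models against models adding baseline mechanism and baseline FMD:

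| Baseline r | Carry-over, planned | Carry-over, adjusted | Stable traits, planned | Stable traits, adjusted |
|---|---|---|---|---|
| −0.1 | 4%–9% | 4%–7% | 16%–28% | 4%–9% |
| −0.2 | 7%–20% | 4%–6% | 54%–75% | 8%–13% |
| −0.3 | 12%–37% | 4%–7% | 74%–98% | 16%–30% |

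Separate runs with both stabilities set to 0.5 or both to 0.7 gave, at r = −0.2, 7%–26% planned under carry-over, and 59%–77% planned against 8%–17% adjusted under stable traits. Sex and age group were not simulated.

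**Cost of adjusting when mediation is real.** For a true mediator acting through a stable trait at r = −0.2, detection falls from 55%–77% to 7%–16%. For a true visit-level effect of −0.2 it does not fall (54%–74% planned, 55%–79% adjusted), but requiring both versions to be significant gives 39%–66%.

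**The case against.** The analysis is labelled exploratory throughout, and nothing in this trial is decided on it. That stands and limits the weight of the point. It does not soften the rule itself, which says what a mechanism is once the test is significant.

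The size rests on assumption: the same baseline r of −0.2 gives 7%–20% or 54%–75% depending on the structure chosen. That also stands. The passage saying "Substantial literatures indicate that depression is reliably associated with each factor" concerns depression and each factor, not the mechanism–FMD link, and the third-factor remark concerns depression and CVD. Sex and age confound *b* only if they also relate to the mechanism. These passages make the rival explanation plausible but do not quantify it.

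Confounding could also run against a true effect and hide a mediator. That is correct, and it is a further reason for caution with *b*, but it does not stop a false label arising in the other direction.

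The planned change–change correlations remove stable between-person levels. They are useful, but they sit outside the decision rule, and pooled over arms they can reflect treatment effects on both variables.

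The strongest objection is that under stable traits the adjusted models flag a false mediator 8%–13% of the time and a true one 7%–16%, so they cannot tell the two apart. This stands. It is why the adjusted models should sit beside the planned ones rather than replace them, and why the wording has to change as well.

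**Conclusion.** The concern holds. The mediation models carry only arm, no other rule in the plan covers mechanism–FMD confounding, and the stated conclusion goes further than the design supports. Confidence is high that a persisting non-causal correlation passes into *b*. How large that correlation is cannot be learned from the documents. If it fades by 12 months, the false-label rate is modestly raised; if it persists near 0.2, more than half of trials with no mechanism effect would report partial mediation. A false label also needs a real effect of arm on the mechanism. The point bears only on the exploratory mechanism conclusions and is a low-cost improvement rather than a threat to the trial's main result.

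**What to change.** 1. Fit the *a* and *b* models a second time with baseline mechanism, baseline FMD, sex and age group added, and report them beside the planned models. Name a mechanism only with both results shown, and do not require both to be significant. Apply the same rule to the supplemental mediation analyses where a baseline value exists.
2. Replace the categorical conclusion with: consistent with partial mediation, assuming no unmeasured mechanism–outcome confounding. If the two versions disagree, say that the data cannot separate a pre-existing shared trait from mediation through a stable trait.
3. Optionally, report the residual mechanism–FMD correlation at which the limits for *ab* first include zero, with no fixed cut-off.
4. Optionally, show the change–change correlations adjusted for arm as well as raw. The raw ones are not an error for a question about association.

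The cost is SAP wording, a few model terms and a second column in the mediation table. The baseline values are already collected at the pre-treatment visit (section 5.0). Adjustment protects only in part, because a single baseline measures a trait with error and confounding that arises after baseline is untouched. It can also sharply cut power for a mediator that acts through a stable trait.

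### The Aim 2 mediation rule tests each mechanism alone, so a marker with no effect on FMD can borrow the effect of depressive symptoms or of its paired marker and be labelled a partial mediator

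*Combined protocol and SAP*

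**What the plan says.** The mediation steps are in section 8.0, Statistical Analyses, under Aim 2. The *a* coefficient comes from regressing each mechanism on treatment group. For *b*, "we will perform linear regressions with 12-month level of each mechanism predicting 12-month FMD in the presence of treatment group". The product *ab* is then tested for each mechanism with asymmetric confidence limits, and the decision rule is: "If this test is significant, the selected mechanism is a partial mediator of the treatment effect on 12-month FMD". No other mechanism and no baseline value is named in the *b* model. The general rule is "All tests will be two-tailed with $p < .05$ considered significant", and no multiplicity adjustment is stated.

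The mechanisms are SCL-20, high-frequency heart rate variability, IL-6, CRP, BTG and PF4. Inflammation and platelet activation are each measured by a pair of markers (section 5.0, Assessments). The conceptual framework in section 1.0 proposes that "treatment-related reductions in depressive symptoms (paths a and b) will result in decreases in the atherogenic factors (paths d and e"), with a further direct path from antidepressants to inflammation and platelets.

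Sections 2.0 and 8.0 both present the mediation work as exploratory. Section 8.0 also plans to correlate changes in symptoms with changes in the physiologic factors, but that result does not enter the mediation model or the rule. The supplemental analyses repeat the Aim 2 approach for behavioural factors, conventional risk factors and depression care variables.

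**The concern.** Randomisation protects *a*. It does not protect *b*, which is an observational association within arm. If symptoms drive several markers after randomisation, those markers are correlated within arm, and a one-mechanism model credits each of them with whatever its correlates do to FMD. Any such marker that treatment also moves can pass the *ab* test without affecting FMD. Adjusting for baseline values would not remove this, because the shared variation arises after randomisation.

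At stake is the reading of Aim 2. Section 1.0 says that knowing the mechanisms would allow adjunctive treatments to be aimed at them, with anti-inflammatory medication as the example. One-at-a-time models cannot separate inflammation from mood, and they can count the same indirect effect several times.

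**Working it through.** **1. The plan's own figure.** Section 8.0 states "we need 88 patients (44 per arm) to detect a group difference in FMD of 1.7"% (d = 0.61), "assuming a power level of 0.80 and a Type I error of 0.05". Normal approximation: n per arm = 2(1.960 + 0.842)²/0.61² = 42.2, so 43. The noncentral t gives 43.17, so 44 per arm and 88 in all, as stated. With 86 per arm, 0.61 × √43 = 4.00 gives power 0.98, and 0.43 × √43 = 2.82 gives 0.80, as stated. The text says "we will have 172 completers ($220 \times .80$) for FMD", but 220 × 0.80 = 176; the difference is immaterial here (step 5). No operating characteristic is given for the mediation test.

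**2. Inputs.**
- From section 8.0: treatment effects of 0.69 SD (depressive symptoms), 0.52 (heart rate variability), 0.43 (IL-6), 0.78 (CRP), 0.46 (BTG, the lower of two) and 0.87 (PF4); total FMD effect 0.61; N = 172.
- Assumed, because the documents give neither: the within-arm correlation r between the inert marker and the true mediator, and the true mediator's effect β on FMD (SD per SD).

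**3. Closed-form approximation.** With symptoms omitted, the inert marker's *b* has expectation r × β. Its standard error is about √[(1 − (rβ)²)/169]. The standard error of *a* is √(4/172) = 0.1525. The labelling rate is roughly the chance that *a* and *b* are both significant.
- *a* = 0.43: z = 2.82, probability 0.80. *a* = 0.78: z = 5.11, probability above 0.99.
- r = 0.5, β = 0.3: *b* = 0.15, SE 0.076, z = 1.97, probability 0.50. Labelling rate 0.41 to 0.50.
- r = 0.3, β = 0.3: *b* = 0.09, SE 0.077, z = 1.17, probability 0.22. Labelling rate 0.17 to 0.22.
- r = 0.1, β = 0.3: *b* = 0.03, z = 0.39, probability 0.07. Labelling rate 0.05 to 0.07.

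**4. Simulation of the plan's test** (1,500–2,000 trials per scenario, asymmetric 95% limits for *ab*). Labelling rate for one inert marker; each range runs from *a* = 0.43 to *a* = 0.78.

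| β | r = 0.1 | r = 0.3 | r = 0.5 |
|---|---|---|---|
| 0.2 | 4–6% | 9–12% | 19–27% |
| 0.3 | 5–6% | 16–23% | 38–51% |
| 0.4 | 6–9% | 27–34% | 57–73% |

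The approximation and the simulation agree. If treatment does not move the marker, the rate is 1.4% (r = 0.5, β = 0.3). With the true mediator in the same model, it is about 3–6% whatever r is. For a marker pair (IL-6 true, CRP inert, β = 0.3), the plan's test labels CRP in 23% of trials at r = 0.3 and 52% at r = 0.5.

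**5. All six mechanisms, only SCL-20 true, β = 0.3.** At least one of five inert markers is labelled in 20% (r = 0), 24% (0.1), 41% (0.2), 58% (0.3) and 81% (0.5) of trials. At N = 176 and r = 0.3 it is 57%. In a joint model it is 18–20%, which is multiplicity alone: 1 − (1 − 0.043)⁵ = 0.20.

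**6. Baseline adjustment** (separate runs, β = 0.35). Adding baseline mechanism and baseline FMD changes the rate from 18% to 22% (r = 0.3, *a* = 0.43), from 49% to 54% (r = 0.5, *a* = 0.43) and from 61% to 62% (r = 0.5, *a* = 0.78). It does not help.

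**7. Power cost of joint modelling.** With six mechanisms and β = 0.3, power for the true mediator falls from 0.98 to 0.94 at r = 0.3 and from 0.97 to 0.85 at r = 0.5. With β = 0.2 and r = 0.5 it falls from 0.75 to 0.51.

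**The case against.** A reader might infer that, if the plan's framework is right, the rule will mislabel bystanders. The documents do not support that. In the framework symptoms act through the physiologic factors, so those markers are mediators. The rates above describe a marker that turns out to be inert.

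A reader might also infer that the joint model should be the only route to the label. That does not follow either. Suppose symptoms act only through five markers, each carrying an assumed 0.15 SD of FMD per SD, with a symptom–marker correlation of 0.5. Detection of each true marker then falls from about 0.8–0.98 in the single models to roughly 0.3–0.47 in the joint model, and detection of symptoms falls from 100% to 4%. In a chain from symptoms to IL-6 to PF4 to FMD, detection of IL-6 falls from 50% to 4%, because the joint model conditions on its downstream step. This part of the objection stands, and it limits the remedy.

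It also stands that r and β are assumed, that inflation is slight at r = 0.1, and that the work is labelled exploratory. The planned correlations of symptom change with marker change would show readers the shared variation. None of this alters the decision rule, which is categorical and takes no account of those correlations.

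**Conclusion.** The concern holds as a conditional one. The single-mechanism models and the unconditional label are in the text, and the plan's own framework supplies the common cause. A claim that mislabelling will happen often is not supported, because the documents give neither the correlations nor the *b* paths. Over β from 0.2 to 0.4, the rate per inert marker runs from near nominal at r = 0.1 to between about one in five and three in four at r = 0.5, and it requires that treatment moves the marker. It is lower if a single sibling marker, rather than symptoms, drives FMD: 6–8% at r = 0.3 and 15–22% at r = 0.5 with a slope of 0.35.

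Nor should anyone read this as a defect in the primary FMD comparison or in Hypotheses 2–5, which are direct comparisons between arms. What is affected is the interpretation of the exploratory mediation results, and of the supplemental analyses that reuse the method.

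**What to change.** 1. For each physiologic marker, add 12-month SCL-20 to the *b* model, since the framework places symptoms upstream. With an assumed slope of 0.35, this brings the labelling rate for an inert marker to about 2–7%. It does not deal with borrowing between paired markers, hence item 2.
2. Report one multiple-mediator model with all mechanisms beside the single-mediator results.
3. Replace the labelling rule with wording such as: a significant *ab* is consistent with mediation; for each marker the report states whether the indirect effect persists after adjustment for SCL-20 and in the joint model; a result seen only in the single-mediator model is described as unadjusted and possibly due to correlated mechanisms.
4. Keep the single-mediator model for SCL-20, whose total indirect effect runs through the markers. Do not make the joint model the sole route to a mediation statement.

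The change needs SAP wording and a few more regressions, with no new data. Its costs are lower power for weak or highly correlated mediators (step 7 and the five-marker example) and conditioning on downstream steps in the joint model. The adjusted models still assume no unmeasured common causes of mechanism and FMD.
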